5.2 What this trial will add

This trial has been designed to fulfil the regulatory requirements for licensing of a nebulizer/vaccine combination device, if the immunogenicity of aerosolized measles vaccination is shown to be non-inferior to subcutaneous vaccine in the target age group, and has an acceptable safety profile. By conducting the trial in a setting where the new delivery device would be used, existing public health surveillance systems will be strengthened, capacity will be built in the trial area for conducting large scale clinical trials and for the handling and serological processing of large numbers of blood samples.

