5.3.2 Safety

To describe the frequency of adverse events following measles aerosol and subcutaneous vaccination.

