11.1.3 Statistical methods, safety

- Primary analysis: proportion (with 95% CI) with any adverse events in aerosol group and in subcutaneous group;
- Secondary analysis: proportions (with 95% CI) of individual adverse events.

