12.1.3 Safety

Primary analysis is proportion (95% CI) with any adverse events in aerosol group with subcutaneous group;

Secondary analysis will describe frequencies of individual adverse events (proportions with 95% CI).

An interim analysis of safety data will be completed. For this analysis, the DSMB will use data from the first 100 children in each arm to complete 91 days of follow up. This will be done as soon as possible after these data are available.

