The primary efficacy analysis for safety includes all children vaccinated, according to the route of vaccination that they received and with at least one safety assessment.

In addition, we will summarize explicitly any severe reactions or serious adverse events (SAE) in children vaccinated by the wrong route.

11.5 Timing of Analyses:

The primary efficacy analysis will be conducted after the last enrolled participant completes the day 91 follow up visit.

Every 3 months the data will be analyzed and a report will be made available for the DSMB. This report will focus on safety.

11.6 Method for Handling Missing Data:

For the primary efficacy analysis there is no plan to impute data values for participants who do not complete follow up visits.

For the PP dataset, missing values will be treated as missing at random. However, preliminary analyses such as age, sex, baseline immunogenicity distribution will be studied between the two groups to examine the validity of this assumption.

For the assessment of immunogenicity, missing values (e.g. no blood taken) are treated as if they are missing at random. The OD values for blood samples taken outside the specified time limits will be treated as missing values.

Note that missing values at 91 days post-vaccination and at other time points will be considered for further analyses. The missing information will be handled by best and worst case scenario methods. Where blood specimens are taken outside the recommended time interval, these results will still be used.

11.7 Significance Level:

This is a non-inferiority trial and the confidence interval approach will be used to determine the trial outcome. For additional analyses, such as those adjusting for covariates, we will not use a fixed 'statistical significance' level for reasons described by Sterne and Davey Smith (3). For analyses that require the calculation of p values, we will base our interpretation on examination of the effect size, confidence interval and p value.

11.8 Safety:

We will estimate the proportions (with 95% CI) of AE in each arm according to the definitions of the primary and secondary safety outcomes (Refer section 8.7 in the protocol).

SOP VEL 1/1:	Statistical Analysis Plan	Page 10 of 61
September 11, 2012		

11.9 Covariates to be examined:

Covariates of interest are as follows:

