	n		% (95% CI) for difference		
	AER	SC	AER	SC	
Seropositivity at day 0					
Seropositivity at day 28					
Seropositivity at day 91					
Seropositivity at day 364					

12.3 Risk factor Analyses:

As covariates for inclusion in multivariable analyses: age; weight for age; sex; day 0 antibody titre; study site; crying when vaccine given (aerosol arm only); presence of respiratory tract symptoms at time of vaccination (aerosol arm only).

	Seropositivity [*]					
Risk Factors/Covariates	OR	95%CI	Р			
Age (months):	•					
9	1.0					
10						
11						
11.99						
Sex (Male)						
Usual health care provider						
Government	1.0					
Private						
Non-governmental organization						
others						
Weight for Age						
Normal	1.0					
Abnormal						
Height for Age						
Normal	1.0					
Abnormal						
Day 0 Antibody Titre						
Sites:						
Vadu	1.0					
Pabal						
Talegoan Dhamdhere						
Nhavare						
Chakan						
Shel Pimpalgaon						
Wagholi						
Alandi						
Crying when vaccine given (yes):						
Respiratory Track Symptoms at the time of vaccination (Yes)						
Any abnormality discovered on systematic examination(Yes)						
Pre existing medical condition(Yes)						

 Table 12.3.1: Risk Factors for Seronegative of Aerosol Arm children

*Modelled for seronegatives.

SOP VEL 1/1:	Statistical Analysis Plan	Page 32 of 61
September 11, 2012		

Phase II/III	WHO Measles Aerosol Vaccine	Protocol
Clinical Trial	Project	WHO/MAP/IN/002

13.0 Safety Analyses:

13.1: Reactogenic Events:

Table 13.1.1A (1): Frequency of adverse events reported during the first 30 minutes after vaccination

	Aerosol				Subcutaneous			
Adverse Events	Number	% of AE	95% percenta	95% CI for ercentage of AE Nu		% of AE	95% CI for percentage of AE	
	OI AES		Lower CI	Upper CI	OI AES		Lower CI	Upper CI

 Table 13.1.1A (2): Number of subjects experiencing at least one adverse event during the first 30 minutes after vaccination

	Aerosol				Subcutaneous			
Adverse Events	Number of persons	Number of persons		95% CI for Population		Proportion in	95% CI for Population	
having AE [#]	population ** (in %)	Lower CI	Upper CI	having AE [#]	** (in %)	Lower CI	Upper CI	

[#]One subject may have more than one AE. So, 'Number of persons having AE' counts expected to overlap

Phase II/III	WHO Measles Aerosol Vaccine	Protocol
Clinical Trial	Project	WHO/MAP/IN/002

Table 13.1.1B (1): Frequency of adverse events reported from 31 minutes 14 days after

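### The safety tables give no aerosol-minus-subcutaneous difference and no per-child result to day 91, and they put confidence intervals on shares of events

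*Supplement*

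**What the plan says.** Protocol 5.3.2 sets the primary safety objective: "To describe the frequency of adverse events following measles aerosol and subcutaneous vaccination". Protocol 5.2 ties licensure to non-inferior immunogenicity and to a product that "has an acceptable safety profile". No numerical safety criterion or margin is given.

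The primary safety outcome is AEs up to and including day 91 (protocol 6.2.2.1, SAP 6.2.1). Protocol 11.1.3 analyses it as "Primary analysis: proportion (with 95% CI) with any adverse events in aerosol group and in subcutaneous group". Protocol 12.1.3 has "Primary analysis is proportion (95% CI) with any adverse events in aerosol group with subcutaneous group", which is unclear in its last words but names no difference or ratio. SAP 11.8 repeats the per-arm plan: "We will estimate the proportions (with 95% CI) of AE in each arm according to the definitions of the primary and secondary safety outcomes".

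SAP 11.4 defines the safety set as treated: "The primary efficacy analysis for safety includes all children vaccinated, according to the route of vaccination that they received".

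SAP 13.1 gives two tables for each of six windows (0-30 minutes, 31 minutes to day 14, days 15-28, 29-56, 57-91 and 92-364):
- Tables 13.1.1A-F (1) count events and carry a column headed "95% CI for percentage of AE".
- Tables 13.1.1A-F (2) count children with at least one AE, with a proportion and interval per arm. A footnote accepts that one child may have several AEs.

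Serology Tables 12.1.3 to 12.1.6 each have a column for the aerosol-minus-subcutaneous difference with its 95% CI. No AE table in SAP 13, SAP 14 or the SAP's DSMB appendix has one.

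**The concern.** Three gaps arise together.

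1. **No contrast.** A reader who wants to know whether the aerosol causes more AEs than the injection has to compare two intervals by eye. Overlap of two 95% intervals is a poor guide to whether the difference is compatible with zero, and it gives no estimate of how large the difference might be.
2. **No table for the primary safety outcome.** A child with AEs in two windows appears in both, so windowed counts of children cannot be added to give any AE by day 91.
3. **Intervals on event shares.** The unit sampled is the child, not the event. A binomial interval on events has the wrong width unless events within a child are independent. The total number of events in an arm is itself an outcome, so a share can move when the risk has not.

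At stake is whether the second leg of the licensing case is reported in a form that answers the question put to it.

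**Working it through.** **The plan's own figure.** SAP Table 8.2.1 gives an upper limit of 0.37% (1 in 270) for 0 events in 1000 children. The exact binomial upper limit is 1 - 0.025^(1/1000) = 0.00368, or 0.37%, so it reproduces. For 800 children, 1 - 0.025^(1/800) = 0.46%, as stated. These are single-arm precisions; neither document states a precision for a between-arm safety difference.

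**Method for the difference.** SAP 11.1 names the Wilson score method for the primary outcome and cites the comparison of interval methods for a difference between proportions. With Wilson limits (l, u) for each arm and d = p1 - p2, the Newcombe interval is

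- lower = d - sqrt[(p1 - l1)² + (u2 - p2)²]
- upper = d + sqrt[(u1 - p1)² + (p2 - l2)²]

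**Example 1: 1000 per arm (the planned number), rates assumed.** Aerosol 130/1000, Wilson 11.06% to 15.23%. Subcutaneous 100/1000, Wilson 8.29% to 12.02%. The arm intervals overlap.

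- d = 3.0 points
- lower = 3.0 - sqrt(1.94² + 2.02²) = 3.0 - 2.80 = 0.20
- upper = 3.0 + sqrt(2.23² + 1.71²) = 3.0 + 2.81 = 5.81

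The difference interval excludes zero although the arm intervals overlap.

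**Example 2: data in the protocol.** Protocol 4.3.2 reports conjunctival inflammation in 34/59 aerosol and 19/55 subcutaneous infants (p = 0.01). Wilson intervals are 44.9% to 69.4% and 23.4% to 47.7%, which overlap. The difference is 57.6 - 34.5 = +23.1 points, Newcombe 4.8 to 39.3.

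**What the missing column would show at 1000 per arm, equal assumed rates.**

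| Rate in both arms | 95% CI for difference (points) |
|---|---|
| 1% | -0.95 to +0.95 |
| 2% | -1.28 to +1.28 |
| 5% | -1.94 to +1.94 |

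So the trial can bound the excess risk usefully, but the planned tables do not say so.

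**Primary outcome to day 91.** For windowed per-child proportions, the proportion with any AE lies between the largest window value and the sum of the windows (at most 100%). If 30% of children had an AE in one window and 20% in the next (assumed), any AE over both lies anywhere from 30% to 50%. The Total rows of Tables 13.2.1 and 13.3.1 do not help: they count events, and they include days 92-364, which apply to Vadu only.

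**Event-share intervals.** The SAP names no interval method for these tables, does not define the denominator of the percentage, and does not say how recurrences are counted. The direction of the error depends on that:

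- *Events of one type cluster in a child.* With m events per child and within-child correlation r, the variance is 1 + (m - 1)r times binomial. For m = 4 and r = 0.3 (assumed) this is 1.9, and a binomial interval is 1 - 1/sqrt(1.9) = 27% too narrow. In a simulation (1000 children, mean 2 AEs each, 20% share), coverage of a nominal 95% Wilson interval fell from 94.7% at correlation 0.01 to 80.2% at 0.33.
- *Each type is counted at most once per child per window.* With m distinct events and share s, the number of fevers in a child is 0 or 1 with mean ms, and the variance ratio is (1 - ms)/(1 - s). For m = 4 and s = 0.2 this is 0.2/0.8 = 0.25. A simulation with about 2.5 distinct events per child gave about 0.5. The interval is then too wide.

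**A share is not a risk.** 200 fever events are 20% of 1000 AEs but 13.3% of 1500 AEs, with the same number of fevers.

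**The case against.** The strongest defence is that the plan does what its objective asks. The safety objective is to describe, no comparative safety criterion is set, and per-arm proportions with intervals are a description. That stands: the missing contrast is a weakness against the licensing aim, not a breach of the objective.

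Four stronger readings are tempting, and the documents do not support them.

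- *The trial never estimates a safety difference.* SAP 11.9 plans logistic regression for binary end points with study arm included, which could be read to cover AEs, although the only regression shell (Table 12.3.1) models seronegativity in the aerosol arm. A difference can also be computed by hand from each per-child table. It is unplanned, not impossible.
- *The primary safety outcome is omitted.* SAP 11.8 commits in words to the defined outcomes, and SAP 9.2 leaves the final table format open until the pre-analysis review. The gap is in the shells. Nor is every safety table windowed: Tables 13.4.1 and 14.0.4 are not.
- *The event-share intervals are too narrow by a known amount.* The 27% figure needs an assumed positive correlation. Under distinct-type counting the error reverses.
- *The missing figure is the randomised difference.* The safety set is as treated, so a difference column there alone would not be a randomised contrast.

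It is also fair to say that 13% v 10% is a borderline example. At 800 per arm the same rates give -0.13 to 6.14, which includes zero. Its use is to show that overlap misleads, not to argue for a test.

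**Conclusion.** The point holds as a reporting weakness worth correcting before analysis. No aerosol-minus-subcutaneous difference is tabulated for any AE, although serology gets one by a method the SAP already cites. No shell gives children with any AE to day 91. The intervals on percentages of events are unreliable in a direction that the SAP's silence on counting rules leaves unknown.

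The size of the first gap is shown by the two examples: +3.0 points (0.2 to 5.8) behind overlapping arm intervals at 1000 per arm, and +23.1 points (4.8 to 39.3) in the protocol's own conjunctival data. The 13% and 10% rates are assumed; the conjunctival counts come from the protocol. The event-share variances (from about 0.25 to 2.3 times binomial) rest entirely on assumed event counts and correlations, and are illustrations, not bounds.

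Nothing here affects the immunogenicity analysis or the trial's size.

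**What to change.** In SAP 11.8 and 13.1:

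- (a) Keep the event counts in Tables 13.1.1A-F (1) and drop the confidence intervals on percentages of events.
- (b) Add to Tables 13.1.1A-F (2) the aerosol-minus-subcutaneous risk difference with a Newcombe 95% CI, in the as-treated set and, as a sensitivity analysis, by randomised arm.
- (c) Add per-child rows over days 0-91 for any AE, any moderate or severe AE, and any SAE.

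Present these as estimates without a significance threshold, in line with SAP 11.7. The cost is a few columns and rows from data already collected. The small downside is many intervals without multiplicity control, which labelling them descriptive deals with.

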12.1. Efficacy Analyses: Immunogenicity

 Table 12.1.1A: Results of ELISA and PRNT, by study group, per-protocol analysis

	Baseline		Day	y 91
	AER	SC	AER	SC
	n=	n=	n=	n=
ELISA result (optical density)				
Median				
Interquartile range				
Min – Max				
Geometric mean titre				
95% CI	n=	n=	n=	n=
PRNT result (mIU/ml)				
Median				
Interquartile range				
Min – Max				
Geometric mean titre				
95% CI				

Legend:

AER – aerosol; SC - subcutaneous

For PRNT titre, includes subjects whose OD values are < 0.1 and all from Vadu site

SOP VEL 1/1:	Statistical Analysis Plan	Page 24 of 61
September 11, 2012		

	Baseline		Day 91	
	AER	SC	AER	SC
	n=	n=	n=	n=
ELISA result (optical density)				
Median				
Interquartile range				
Min – Max				
Geometric mean titre				
95% CI	n=	n=	n=	n=
PRNT result (mIU/ml)				
Median				
Interquartile range				
Min – Max				
Geometric mean titre				
95% CI				

Table 12.1.1B: Results of ELISA and PRNT, by study group, ITT analysis

Note: For PRN titre, the subjects whose OD values are < 0.1 and from Vadu site

12.1.2: Day 91 ELISA and PRNT results

Table 12.1.2A: Aerosol Group

	PRNT <120	PRNT >=120	PRNT not done	Total
Day 91 ELISA <0.1				
Day 91 ELISA >=0.1				
Day 91 ELISA Not done				
Total				

Legend:

Boxes highlighted in yellow represent results classified as seropositive at day 91

Phase II/III	WHO Measles Aerosol Vaccine	Protocol
Clinical Trial	Project	WHO/MAP/IN/002

Table 12.1.2B: Subcutaneous Group

	PRNT <120	PRNT >=120	PRNT not done	Total
Day 91 ELISA <0.1				
Day 91 ELISA >=0.1				
Day 91 ELISA Not done				
Total				

Legend:

Boxes highlighted in yellow represent results classified as seropositive at day 91

Table 12.1.3: Measles seropositive at day 91 post-vaccination (all infants) and difference in positivity between study arms

	AER n/N	AER%, 95% CI	SC n/N	SC%, 95% CI	Difference (AER- SC), 95% CI*
Seropositive at day 91					

Legend:

AER – aerosol; SC – subcutaneous;

* This difference is used to interpret non-inferiority, estimated by Wilson score method (5) (6).

Table 12.1.4A: Comparison of serological outcomes, by study group and time of sample collection: **Per Protocol cohort**

	AER		SC		Difference	
Time point	n	%	n	%	(AER-SC) 95% CI	
Day 0, seropositive						
Day 91, seropositive						
Day 91, seroconversion						

Legend:

AER – aerosol; SC - subcutaneous

Phase II/III	WHO Measles Aerosol Vaccine	Protocol
Clinical Trial	Project	WHO/MAP/IN/002

Table 12.1.4B: Comparison of serological outcomes, by study group and time of sample collection: **ITT cohort**

	AER		SC		Difference	
Time point	n	%	n	%	(AER-SC) 95% CI	
Day 0, seropositive						
Day 91, seropositive						
Day 91, seroconversion						

Legend:

AER – aerosol; SC - subcutaneous

Table 12.1.5A: Comparison of serological outcomes, by study group and time of sample collection for Vadu subset: **Per Protocol cohort**

	AER		SC		Difference	
Time point	n	%	n	%	(AER-SC) 95% CI	
Day 0, seropositive						
Day 28, seropositive						
Day 28, seroconversion						

Legend:

AER – aerosol; SC - subcutaneous

Table 12.1.5B: Comparison of serological outcomes, by study group and time of sample collection for Vadu subset: **ITT cohort**

	AER		SC		Difference		
Time point	n	%	n	%	(AER-SC) 95% CI		
Day 0, seropositive							
Day 28, seropositive							
Day 28, seroconversion							

Legend:

AER – aerosol; SC - subcutaneous

Table 12.1.6A: Comparison of serological outcomes, by study group and time of sample collection for Vadu subset: **Per Protocol cohort**

Time point		AER		SC	Difference	
		%	ó n %		(AER-SC) 95% CI	
Day 0, seropositive						
Day 364, seropositive						
Day 364, seroconversion						

Legend:

AER - aerosol; SC - subcutaneous

SOP VEL 1/1:	Statistical Analysis Plan	Page 27 of 61
September 11, 2012		

Phase II/III	WHO Measles Aerosol Vaccine	Protocol
Clinical Trial	Project	WHO/MAP/IN/002

Table 12.1.6B: Comparison of serological outcomes, by study group and time ofsample collection for Vadu subset: **ITT cohort**

Time point		AER		SC	Difference	
		%	n	%	(AER-SC) 95% CI	
Day 0, seropositive						
Day 364, seropositive						
Day 364, seroconversion						

Legend:

AER – aerosol; SC - subcutaneous

Table 12.1.7: Day 0 and 91 ELISA and PRNT results with Sero-Conversion. (highlighted in yellow)

	Day 91									
				ELISA <().1]	ELISA >:	=0.1	ELISA Not done	
		PRNT	<120	>=120	Not done	<120	>=120	Not done	<120	>=120
	ELISA	<120								
	<0.1	>=120								
y 0)		Not done								
le (Da	ELISA	<120								
Baselin	>=0.1	>=120								
		Not done								
	ELISA	<120								
	Not done	>=120								
		Not done								

Note: Highlighted in grey are the ones, which are "Not Applicable". That is, which are seropositive or unknown at baseline

Phase II/III	WHO Measles Aerosol Vaccine	Protocol
Clinical Trial	Project	WHO/MAP/IN/002

		GMTs		
	AER	SC	Ratio AER/SC	95% CI for
				ratio
Day 0				
OD (all)				
Day 91				
OD (all)				
OD				
(OD >0.1)				
PRNT				
(OD<0.1)				

Table 12.1.0: Geometric mean titles, pre-vaccination and at day 91 101 an infant	Table 12.1.8:	Geometric mean	titres, pre-v	vaccination and	l at dav	y 91 fc	or all infants
---	---------------	----------------	---------------	-----------------	----------	---------	----------------

12.2 Secondary End Point (For infants from Vadu in 28 and 364 days subset): ITT Cohort

12.2.1*Analysis:* Geometric mean titres and ODs at days 0, 28, 91 and 364 to describe evolution of antibody response;

Table 12.2.1.1A: Descriptive statistics of infants age 9 to 11.99 months at vaccination and change in ELISA titer for subset of subjects at Vadu followed to day 364

	Baseline		Day	Day 28 Da		y 91	Day 364	
	AER	SC	AER	SC	AER	SC	AER	SC
	n=	n=	n=	n=	n=	n=	n=	n=
ELISA Titer: (\triangle OD)								
Median								
Min – Max								
GMT								
95% CI								

Table 12.2.1.1B: Descriptive statistics of infants age 9 to 11.99 months at vaccination and change in PRN titer for subset of subjects at Vadu followed to day 364

	Bas	Baseline		y 28	Day	⁷ 91 Day		y 364	
	AER	SC	AER	SC	AER	SC	AER	SC	
	n=	n=	n=	n=	n=	n=	n=	n=	
PRN Titer: (mIU/ml)									
Min – Max									
GMT									
95% CI									

SOP VEL 1/1:	Statistical Analysis Plan	Page 29 of 61
September 11, 2012		

Phase II/III	WHO Measles Aerosol Vaccine	Protocol
Clinical Trial	Project	WHO/MAP/IN/002

Table 12.2.1.2: Geometric mean titres, pre-vaccination and at days 28, 91, 364 for
infants in the Vadu subset

GMTs							
	AER			SC	Ratio	95% CI	
	n	GMTs	n	GMTs	AER/SC		
28 days subset							
Day 0 OD							
Day 28 OD							
Day 91 OD							
Day0 PRNT							
Day 28 PRNT							
Day 91 PRNT							
364 days subset							
Day 0 OD							
Day 91 OD							
Day 364 OD							
Day 0 PRNT							
Day 91 PRNT							
Day 364 PRNT							

12.2.1.3: Seropositivity at 364 days in infants with PRNT \geq 120 mIU/ml at day 91

12.2.1.3A: Aerosol group

			Day 364	
1	PRNT	<120	>=120	Total
y 9.	<120			
Day	>=120			
	Total			

12.2.1.3B: Subcutnaeous group

			Day 364	
1	PRNT	<120	>=120	Total
y 9.	<120			
Day	>=120			
	Total			

SOP VEL 1/1:	Statistical Analysis Plan	Page 30 of 61
September 11, 2012		

Phase II/III	WHO Measles Aerosol Vaccine	Protocol
Clinical Trial	Project	WHO/MAP/IN/002

12.2.1.4: Seropositivity at days 0, 28, 91 and 364 and changes betw	een these time
points	

Table 12.2.1.4.1:	Measles	seropositivity at	days () 28	91	and 364.
1 auto 12.2.1.7.1.	Medsies	scropositivity at	uayov	J, 20,	1	ana 50 4 .

	n		% (95% CI) for difference		
	AER	SC	AER	SC	
Seropositivity at day 0					
Seropositivity at day 28					
Seropositivity at day 91					
Seropositivity at day 364					

12.3 Risk factor Analyses:

As covariates for inclusion in multivariable analyses: age; weight for age; sex; day 0 antibody titre; study site; crying when vaccine given (aerosol arm only); presence of respiratory tract symptoms at time of vaccination (aerosol arm only).

	Seropositivity [*]					
Risk Factors/Covariates	OR	95%CI	Р			
Age (months):	•					
9	1.0					
10						
11						
11.99						
Sex (Male)						
Usual health care provider						
Government	1.0					
Private						
Non-governmental organization						
others						
Weight for Age						
Normal	1.0					
Abnormal						
Height for Age						
Normal	1.0					
Abnormal						
Day 0 Antibody Titre						
Sites:						
Vadu	1.0					
Pabal						
Talegoan Dhamdhere						
Nhavare						
Chakan						
Shel Pimpalgaon						
Wagholi						
Alandi						
Crying when vaccine given (yes):						
Respiratory Track Symptoms at the time of vaccination (Yes)						
Any abnormality discovered on systematic examination(Yes)						
Pre existing medical condition(Yes)						

 Table 12.3.1: Risk Factors for Seronegative of Aerosol Arm children

*Modelled for seronegatives.

SOP VEL 1/1:	Statistical Analysis Plan	Page 32 of 61
September 11, 2012		

Phase II/III	WHO Measles Aerosol Vaccine	Protocol
Clinical Trial	Project	WHO/MAP/IN/002

13.0 Safety Analyses:

13.1: Reactogenic Events:

Table 13.1.1A (1): Frequency of adverse events reported during the first 30 minutes after vaccination

	Aerosol				Subcutaneous			
Adverse Events	Number	% of AE	95% percenta	95% CI for ercentage of AE Nu		% of AE	95% CI for percentage of AE	
	OI AES		Lower CI	Upper CI	OI AES		Lower CI	Upper CI

 Table 13.1.1A (2): Number of subjects experiencing at least one adverse event during the first 30 minutes after vaccination

	Aerosol				Subcutaneous			
Adverse Events	Number of persons	Number of persons		95% CI for Population		Proportion in	95% CI for Population	
having AE [#]	population ** (in %)	Lower CI	Upper CI	having AE [#]	** (in %)	Lower CI	Upper CI	

[#]One subject may have more than one AE. So, 'Number of persons having AE' counts expected to overlap

Phase II/III	WHO Measles Aerosol Vaccine	Protocol
Clinical Trial	Project	WHO/MAP/IN/002

Table 13.1.1B (1): Frequency of adverse events reported from 31 minutes 14 days after
vaccination and number of subjects experiencing at least one adverse event

		A	Aerosol		Subcutaneous			
Adverse Events	Number	% of	95% CI for		Number % of AF		95% CI for	
	of AEs	AE	Lower CI	Upper CI	of AEs	70 OI AL	Lower CI	Upper CI

 Table 13.1.1B (2): Number of subjects experiencing at least one adverse event from 31 minutes to 14 days after vaccination

	Aerosol				Subcutaneous			
Adverse Events of		Proportion in	95% CI for Population		Number of persons	Proportion in	95% CI for Population	
persons having AE [#]	persons having AE [#]	population ** (in %)	Lower CI	Upper CI	having AE [#]	population ** (in %)	Lower CI	Upper CI

[#]One subject may have more than one AE. So, 'Number of persons having AE' counts expected to overlap

SOP VEL 1/1:	Statistical Analysis Plan	Page 34 of 61
September 11, 2012		

Phase II/III	WHO Measles Aerosol Vaccine	Protocol
Clinical Trial	Project	WHO/MAP/IN/002

Table 13.1.1C (1): Frequency of adverse events reported from 15 days to 28 days after vaccination

	Aerosol				Subcutaneous			
Adverse Events	Number	% of AE	95% percenta	CI for age of AE	Number	% of AE	95% percenta	CI for age of AE
	of AEs	,,,,,,,,,,,,,,,,,,,,,,,,,,,,,,,,,,,,,,,	Lower CI	Upper CI	of AEs	/0 01 112	Lower CI	Upper CI

Table 13.1.1C (2): Number of subjects experiencing at least one adverse event from 15 days to 28 days after vaccination

		Aeros	sol		Subcutaneous				
Adverse Events	Number of	aber Proportion of in		95% CI for Population		Proportion in	95% (Popul	CI for ation	
	persons having AE [#]	population ** (in %)	Lower CI	er Upper I CI	having AE [#]	(in %)	Lower CI	Upper CI	

[#]One subject may have more than one AE. So, 'Number of persons having AE' counts expected to overlap

SOP VEL 1/1:	Statistical Analysis Plan	Page 35 of 61
September 11, 2012		

Phase II/III	WHO Measles Aerosol Vaccine	Protocol
Clinical Trial	Project	WHO/MAP/IN/002

Table 13.1.1D (1): Frequency of adverse events reported from 29 days to 56 days after vaccination

	Aerosol				Subcutaneous			
Adverse Events	Number	% of AE	95% percenta	CI for ige of AE	Number	% of AE	95% percenta	CI for ige of AE
	OI AES		Lower CI	Upper CI	OI AES		Lower CI	Upper CI

 Table 13.1.1D (2): Number of subjects experiencing at least one adverse event from 29 days to 56 days after vaccination

		Aeros	sol		Subcutaneous			
Adverse Events	Number Proportion of in		95% CI for Population		Number of persons	Proportion in	95% CI for Population	
	persons having AE [#]	sons population ing ** E [#] (in %)	Upper CI	having AE [#]	population ** (in %)	Lower CI	Upper CI	

[#]One subject may have more than one AE. So, 'Number of persons having AE' counts expected to overlap

SOP VEL 1/1:	Statistical Analysis Plan	Page 36 of 61
September 11, 2012		

Phase II/III	WHO Measles Aerosol Vaccine	Protocol
Clinical Trial	Project	WHO/MAP/IN/002

Table 13.1.1E (1): Frequency of adverse events r	reported from 57 days	s to 91 days after
vaccination		

	Aerosol				Subcutaneous			
Adverse Events	Number	% of AE	95% CI for percentage of AE		Number	% of AE	95% CI for perceptage of AE	
	of AEs	/0 01 112	Lower CI	Upper CI	of AEs	/0 01 112	Lower CI	Upper CI

 Table 13.1.1E (2): Number of subjects experiencing at least one adverse event from 57 days to 91 days after vaccination

		Aeros	sol		Subcutaneous			
Adverse Events	Number Proportion of in		95% CI for Population		Number of persons	Proportion in	95% CI for Population	
	persons having AE [#]	population ** (in %)	Lower Upper CI CI	having AE [#]	population ** (in %)	Lower CI	Upper CI	

[#]One subject may have more than one AE. So, 'Number of persons having AE' counts expected to overlap

SOP VEL 1/1:	Statistical Analysis Plan	Page 37 of 61
September 11, 2012		

Phase II/III	WHO Measles Aerosol Vaccine	Protocol
Clinical Trial	Project	WHO/MAP/IN/002

Table 13.1.1F (1): Frequency of adverse events reported from 92 days to 364 days after	er
vaccination	

	Aerosol				Subcutaneous			
Adverse Events	Number	% of AE	95% percenta	CI for ige of AE	Number	% of AE	95% percenta	CI for age of AE
	OI AES		Lower CI	Upper CI	OI AES		Lower CI	Upper CI

 Table 13.1.1F (2): Number of subjects experiencing at least one adverse event from 92 days to 364 days after vaccination

		Aeros	Subcutaneous					
Adverse Events	Number Proportio of in		95% CI for Population		Number of persons	Proportion in	95% CI for Population	
	persons having AE [#]	s population ** (in %)	Lower CI	Upper CI	having AE [#]	population ** (in %)	Lower CI	Upper CI

[#]One subject may have more than one AE. So, 'Number of persons having AE' counts expected to overlap

SOP VEL 1/1:	Statistical Analysis Plan	Page 38 of 61
September 11, 2012		

13.2: Severity of reactions

The Distribution of Severity of Adverse Events:

Table 13.2.1A: Number of AEs reported according to severity in the Aerosol group

		Severity of A		SAE		
Time Points	Mild n (% of events)	Moderate n (% of events)	Severe n (% of events)	Total	events)	
0-30mins						
31 mins to day 14						
Day15-28						
Day29-56						
Day57-91						
Day 92-364*						
Total						

*Applies to Vadu subset only

Table 13.2.1B: Number of AEs reported according to severity in the Subcutaneous group

Time Points		Severity of A		SAE	
	Mild n (% of events)	Moderate n (% of events)	Severe n (% of events)	Total	n (% of events)
0-30mins					
31 mins to day 14					
Day15-28					
Day29-56					
Day57-91					
Day 92-364*					
Total					

*Applies to Vadu subset only

Phase II/III
Clinical Trial

13.3: Causality

Table 13.3.1A: Number of moderate and severe Adverse Events and relationship to vaccination, Aerosol group

	Relationship to Vaccination						
Time Points	Not Related n (% of events)	Unlikely to be Related n (% of events)	Possible n (% of events)	Probable n (% of events)	Most Probably n (% of events)	Insufficient data to assess n (% of events)	Total
0-30mins							
31 mins to day 14							
Day15-28							
Day29-56							
Day57-91							
Day 92-364*							
Total							

*Applies to Vadu subset only

Table 13.3.1B: Number of moderate and severe Adverse Events and relationship to
vaccination, Subcutaneous Group

	Relationship to Vaccination						
Time Points	Not Related n (% of events)	Unlikely to be Related n (% of events)	Possible n (% of events)	Probable n (% of events)	Most Probably n (% of events)	Insufficient data to assess n (% of events)	Total
0-30mins							
31 mins to day 14							
Day15-28							
Day29-56							
Day57-91							
Day 92-364*							
Total							

*Applies to Vadu subset only

Phase II/III	WHO Measles Aerosol Vaccine	Protocol
Clinical Trial	Project	WHO/MAP/IN/002

13.4: Listing of AEs by subject

Table 13.4.1: AE listing by Subject

subject ID(Sex)	Age (Day)	Vaccinat ed Date	AE	Date of AE onset	Days to start AE	Date of AE stops	Duration of AE existence (in days)	Concomitant Medications given for the Visit	AE treatment outcome

Phase II/III	WHO Measles Aerosol Vaccine	Protocol
Clinical Trial	Project	WHO/MAP/IN/002

14.0 Interim Analyses:

An interim analysis of safety data will be completed for this analysis. This includes only safety assessment events reported within 91 days after vaccination, and no laboratory results will be included. The DSMB will use data from the first 100 children in each arm. This will be done as soon as possible after these data are available.

Table 14.0.1: Frequency of all AEs by study group and time since vaccination

	Time since vaccination																	
Name	Visit 2 0 – 30 mins		Visit 3 31 mins – 3 days		Vi: 4 - 7	Visit 4 4 – 7 days		Visit 5 8 – 10 days		Visit 6 11 – 14 days		sit 7 – 16 1ys	Visit 8 17 – 21 days		Vis 22 - da	it 9 - 28 iys	 To	tal
	AER	SC	AER	SC	AER	SC	AER	SC	AER	SC	AER	SC	AER	SC	AER	SC	AER	SC
Adverse Events Mild, Moderate &Severe*** Anorexia																		
Conjunctivitis																1		
Coryza																		
Cough																		
Crying																		
Diarrhoea																		
Difficulty																		1
Fever																		
Irritability																		
Local reaction																		
Malaise																		
Rash																		
Seizure																		
Shivering																		
Vomit																		
Wheeze																		
Others																		
Total																		
SOP VEL 1/1: Sep 2012		Statistical Analysis Plan							Pag	e 42 of	61							

Phase II/III Clinical Trial	WHO Measles Aerosol Vaccine Project	Protocol WHO/MAP/IN/002

Table 14.0.2: Frequency of AE that have been deemed probably related and most probably related* by study group and time since vaccination

	Time since vaccination													Το	otal			
Name	Vis	sit 2	Vis	it 3	Vis	sit 4	Vis	sit 5	Vis	sit 6	Vis	sit 7	Vis	sit 8	Vis	it 9		
	0 - 30) mins	31 mins	– 3 days	4 – 7	days	8 – 10) days	11 – 1	4 days	15 – 1	6 days	17 – 2	1 days	22 - 2	8 days		
	AER	SC	AER	SC	AER	SC	AER	SC	AER	SC	AER	SC	AER	SC	AER	SC	AER	SC
Adverse Events																		
Mild, Moderate & Severe***																		
Anorexia																		
Conjunctivitis																		
Coryza																		
Cough																		
Crying																		
Diarrhoea																		
Difficulty																		
Fever																		
Irritability																		
Local reaction																		
Malaise																		
Rash																		
Seizure																		
Shivering																		
Vomit																	 	
Wheeze																		
Others																		
Total																		

SOP VEL 1/1:	Statistical Analysis Plan	Page 43 of 61
Sep 2012		

Phase II/III	WHO Measles Aerosol Vaccine	Protocol
Clinical Trial	Project	WHO/MAP/IN/002

Table 14.0.3: Frequency of AE that have been deemed probably related and most probably related* by study group, severity and time since vaccination

Part1: Mild and Moderate counts together

	Time since vaccination												Тс	otal					
Name	Vis 0 - 30	sit 2) mins	Vis 31 mins	sit 3 – 3 davs	Vis 4 – 7	sit 4 ′ davs	Vis 8 – 1	sit 5 0 davs	Vis 11 – 1	sit 6 4 davs	Vis 15 – 1	sit 7 6 davs	Vis 17 – 2	sit 8 1 davs	Vis 22 – 2	sit 9 8 davs			, cui
	AER	SC	AER	SC	AER	SC	AER	SC	AER	SC	AER	SC	AER	SC	AER	SC		AER	SC
Adverse Events Mild or																			
Moderate																			
Anorexia																			
Conjunctivitis																			 
Coryza																			 
Cough																			
Crying																			
Diarrhoea																			
Difficulty																			
Fever																			
Irritability																			
Local reaction																			
Malaise																			
Rash																			
Seizure																			
Shivering																			
Vomit																			
Wheeze																			1
Others	ł	1		1		1	1	1	ł		ł	ł				1			1
Total																			1

SOP VEL 1/1:	Statistical Analysis Plan	Page 44 of 61
Sep 2012		

Phase II/III	WHO Measles Aerosol Vaccine	Protocol
Clinical Trial	Project	WHO/MAP/IN/002

Part 2: Severe counts

	Time since vaccination																		
Name	Vis 0 - 30	sit 2 0 mins	Vis 31 mi da	sit 3 ins — 3 ays	Vis 4 - 7	sit 4 V days	Vis 8 – 10	sit 5 0 days	Vis 11 – 1	sit 6 4 days	Vis 15 – 1	sit 7 .6 days	Visit 8 17 – 21 days		Visit 9 22 – 28 days		••	Το	ital
	AER	SC	AER	SC	AER	SC	AER	SC	AER	SC	AER	SC	AER	SC	AER	SC		AER	SC
Adverse Events Severe***																			
Anorexia																			
Conjunctivitis																			 
Coryza																			
Cough																			
Crying																			
Diarrhoea																			
Difficulty																			
Fever																			
Irritability																			
Local reaction																			
Malaise																			
Rash																			
Seizure																			
Shivering																			
Vomit																			
Wheeze																			1
Others																			1
Total			1																

SOP VEL 1/1:	Statistical Analysis Plan	Page 45 of 61
Sep 2012		

Phase II/III	WHO Measles Aerosol Vaccine	Protocol
Clinical Trial	Project	WHO/MAP/IN/002

Part 3: Serious Adverse Events

								Time s	ince vacc	ination							То	tal
Name	Vis 0 - 30	it 2 mins	Vis 31 mins	sit 3 s – 3 days	Vis 4 – 7	sit 4 ' days	Vis 8 – 10	sit 5) days	Vis 11 – 14	it 6 4 days	Vis 15 – 1	sit 7 6 days	Vis 17 – 2	sit 8 1 days	Vis 22 – 2	it 9 8 days		tai
	AER	SC	AER	SC	AER	SC	AER	SC	AER	SC	AER	SC	AER	SC	AER	SC	AER	SC
Serious Adverse Events**																		
Result in death																		
